STUDY TITLE

Breathing Pattern Variability in Preterm Infants: Effect of Non-invasive Neurally Adjusted Ventilatory Assist (NAVA-NIV) Versus Nasal Intermittent Positive Pressure Ventilation (PC-NIV), a Cross-Over Study.

NCT number: not available yet.

Date of the document, as submitted to local ethical committee: v1.1 of the 27th February 2019

Date of local ethical committee approval: 1st March 2019

Date of translation in English: 29th May 2019

STUDY OBJECTIVES

Primary: To evaluate the effect of NAVA-NIV compared to Nasal Intermittent Positive Pressure Ventilation (PC-NIV) at the same of peak inspiratory pressure in terms of breath-by-breath variability of tidal breathing amplitude in preterm infants < 37+0 weeks+days post-menstrual age.

Secondary: To evaluate the effect of NAVA-NIV compared to Nasal Intermittent Positive Pressure Ventilation (PC-NIV) at the same level of peak inspiratory pressure in terms of variability of the other breathing pattern parameters; lung mechanics; gas exchange; rate of apneic episodes; bradycardia and desaturations; respiratory asynchrony and comfort.

STUDY DESIGN

It will be a monocentric, randomized, cross-over trial.

The setting will be the Neonatal Intensive Care Unit (NICU) of Fondazione IRCCS Cà Granda Ospedale Maggiore Policlinico, Milan, Italy, in collaboration with the Laboratorio di Tecnologie Biomediche – TBMLab, Dipartimento di Elettronica, Informazione e Bioingegneria – DEIB, Politecnico di Milano University, Milan, Italy.

STUDY POPULATION

Preterm infants born < 37 weeks of gestation, requiring non-invasive respiratory support

INCLUSION CRITERIA

- Preterm birth < 37 weeks of gestational age
- Need of non-invasive respiratory support
- Parental consent

EXCLUSION CRITERIA

- Major congenital abnormalities of the cardio-respiratory systems
- Severe Respiratory Failure requiring intubation and mechanical ventilation at the time of the study; pH < 7.25 pCO₂ > 65 mmHg; pulmonary hypertension requiring pharmacological treatment (Nitric Oxide, Sildenafil)
- Hypoxic-Ischaemic Encephalopathy, neurological disorders which may compromise the integrity of the neural transmission from the brain to the diaphragm
- Contraindication to orogastric tube insertion (e.g. oesophageal atresia, gastric perforation...)
- Haemodynamic instability requiring inotropic agents
- Any condition that would expose the patient to undue risk as deemed by the attending physician

STUDY INTERVENTION

Preterm infants matching the inclusion criteria (listed elsewhere) will be enrolled in a cross-over trial of two modes of non-invasive respiratory support: nasal intermittent positive pressure ventilation (PC-NIV) and NAVA NIV (Sevo-n Neonatal Ventilator, Getinge, Solna, Sweden).

In order to compare the two modes at the same level of PIP, a 20-minute registration of ventilator parameters during assistance on NAVA-NIV will allow calculating the mean PIP (peak inspiratory pressure)..

The ventilator settings other than PIP (i.e. FiO₂, PEEP, IT, RR) will be based on the setting optimized by the attending physicians prior to the study entry.

Infants will then receive a randomized sequence of 1-hour assistance by NAVA NIV and 1-hour assistance PC-NIV at the same level of PIP or vice-versa.

FiO₂ will be adjusted in order to maintain SpO₂ 88-93% in infants ≤ 32 weeks of postconceptional age, 90-95% in infants > 32 weeks of postconceptional age.

Infants will receive respiratory support in a standardized supine position during the study period.

RANDOMIZATION

The randomization will be created by generating casual numbers by specific MatLab functions. Closed, opaque, sequentially numbered envelops will be then created by the collaborators from the department of Elettronica, Informazione e Bioingegneria – DEIB, Politecnico di Milano University. After enrolment, physicians will open the envelop containing the sequence of randomization.

ENDPOINTS

PRIMARY

Breath-by-breath variability of tidal breathing amplitude.

Tidal breathing amplitude will be recorded continuously via two, high resolution, small cameras placed inside the infant's incubator and skin (non-invasive) markers. Ventilator parameters (flow, pressure, volume and electrical diaphragmatic activity) will be recorded continuously during the study. Data will be analysed *a posteriori* applying parametric or non-parametric statistical tools depending on the results of normal distribution test and long term correlation properties will be studied by the DFA (Detrended Fluctuation Analysis) technique or similar.

SECONDARY

Breathing pattern variability (Tidal Volume, Respiratory Rate, Inspiratory Time, Duty Cycle)

Ventilator parameters (flow, pressure, volume and the electrical diaphragmatic activity) will be recorded continuously during the study, chest and abdominal volume displacement will be detected by two high-resolution camera-based 3D depth sensors placed in the incubators. The variability of the breathing pattern will be then analyzed by the DFA technique.

Lung mechanics (lung reactance and lung resistance)

Lung mechanics will be measured by mean of the Forced Oscillation Technique (FOT) at the end of each step, by superimposing to the ventilator waveform an oscillatory pressure of small amplitude and high frequency (Fabian, Acutronic Medical Systems AG, Switzerland). Flow and pressure signals will be collected and respiratory mechanics will be evaluated by estimating offline the total respiratory system input impedance and expressed as reactance and resistance.

Gas exchange

Fraction of inspired oxygen (FiO₂), SpO₂ and transcutaneous pCO₂ will be monitored continuously.

Rate of apnoeas, desaturations, bradycardias

Episodes of apnoea, desaturation, and bradycardia will be recorded over each study period

Rate of patient-ventilator asynchronies

Patient-ventilator asynchronies will be calculated by continuous recording of ventilator parameters (flow, pressure, volume and electrical diaphragmatic activity) and by continuous recording of abdominal and chest movements by high resolution cameras placed in the incubators and skin markers on abdomen and chest

Patient's comfort

Patient's comfort will be assessed by the attending nurse at the end of each step by means of the COMFORT scale at the end of each step.

Number of caregiver interventions required

The number of interventions required by the attending personnel during each step will be also recorded: for instance interventions to improve comfort, to adjust the ventilator interface, to optimize the efficacy of respiratory support, suctioning ...

STUDY DURATION/TIME POINTS

The first part of the study will be to determine the mean PIP during NAVA NIV over a 20-minute period, followed by the cross-over, made up of two steps lasting 1 hour each. At the end of each step, a 5-minute measurement by FOT will take place. Data will be assessed at the beginning of the study (t0), every 10 minutes during the first 30 minutes and every 5 minutes during the last 30 minutes.

STATISTICAL ANALYSIS

The sample size of the study was calculated by G-power. 25 patients are needed for a two-tailed power > 0.80 with $\alpha=0.05$, hypothesizing a normal distribution and an effect dimension of 0.59. The effect dimension was calculated considering a correlation among groups = 0.5 and tidal volume variations (used as a quantitative index for characterizing breathing amplitude variations) of newborn infants supported by nasal CPAP (0.79 ± 0.14) and after the application of nasal CPAP at 2 cmH₂O (0.71 ± 0.13) [Zannin, Pediatr Pulmonology 2018].

Measured Variables and Data Analysis

From the flow, pressure, volume and electrical diaphragmatic activity tracings, the breathing patterns will be measured (see above). The end-expiration will be identified by the two small, high resolution camera-based 3D sensors and the skin markers. FiO₂, SpO₂, tc pCO₂ will be also measured. At the end of each step lung resistance (Rrs) and reactance (Xrs) will be assessed by FOT. A dedicated

operator will record the number of episodes of apnea, bradycardia and desaturation. Patient's comfort will be assessed by the COMFORT scale. Mean (or median as appropriate) and SD (or IQR) will be calculated for all the parameters measured. Short-term variability will be determined by the variation coefficient (SD). Long-term correlation will be evaluated by the DFA technique. ANOVA or Friedman test for repeated measurements as appropriate according to data distribution will be used to verify differences in each of the parameters analysed, considering groups.

ETHICS

The present study will be conducted following the ICH/GCP International Conference of Harmonization/Good Clinical Practice rules and all the applicable regulations, including the declaration of Helsinki, June 1964, modified by the World Medical Association General Assembly in Seoul, 2008.

The study protocol has been approved by the local Ethical Committee, Comitato Etico Milano di Area 2, on March 1st 2019.

REFERENCE

- [1] K. Costeloe, E. Hennessy, A. T. Gibson, N. Marlow, A. R. Wilkinson, and for the EPICure Study Group, "The EPICure Study: Outcomes to Discharge From Hospital for Infants Born at the Threshold of Viability," *Pediatrics*, vol. 106, no. 4, pp. 659–671, 2000.
- [2] P. Y. Ancel *et al.*, "Survival and morbidity of preterm children born at 22 through 34 weeks' gestation in France in 2011: results of the EPIPAGE-2 cohort study," *JAMA Pediatr.*, vol. 169, no. 3, pp. 230–238, 2015.

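### Does the age limit in the primary objective conflict with the inclusion criteria in a way that needs a change?

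*Combined protocol and SAP*

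**What the plan says.** The primary objective, under Study Objectives, names its infants as follows: "tidal breathing amplitude in preterm infants < 37+0 weeks+days post-menstrual age". The secondary objective and the title give no age limit.

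Two other headings describe who is studied. Study Population reads "Preterm infants born < 37 weeks of gestation, requiring non-invasive respiratory support". Inclusion Criteria reads "Preterm birth < 37 weeks of gestational age", alongside the need for support and parental consent. None of the exclusion criteria mentions post-menstrual or postnatal age.

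Study Intervention links enrolment to the criteria: "Preterm infants matching the inclusion criteria (listed elsewhere) will be enrolled in a cross-over trial". It adds no age filter. The same section uses age at study once, to choose between two oxygen saturation bands split at 32 weeks. The upper band, "90-95% in infants > 32 weeks of postconceptional age", has no ceiling.

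**The concern.** Gestational age at birth is fixed. Post-menstrual age is gestational age at birth plus the time since birth, so it keeps rising. A 37-week limit on the first is a condition on birth; on the second, it is a condition on the day of study. The objective appears to use the second, while the sections that govern entry use the first.

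If so, the trial could enrol infants whom its primary question does not name. At stake is the scope of the result: a reader of the objective might take it to describe infants studied before 37+0 weeks when some were older. The saturation bands make this look less like a simple slip, because they show that the plan uses age at study as a separate idea.

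**Working it through.** **Setting the texts side by side**

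| Place | Limit | Type of age |
|---|---|---|
| Study Objectives, primary | < 37+0 weeks | post-menstrual (advances after birth) |
| Study Population | < 37 weeks | at birth |
| Inclusion Criteria | < 37 weeks | at birth |
| Exclusion Criteria | none | – |
| Study Intervention, enrolment | refers to the inclusion criteria | at birth |

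**Direction of the mismatch.** Age at study is never less than age at birth. Every infant studied before 37+0 weeks was therefore born before 37 weeks, and the objective's population lies wholly inside the eligible one. Nobody named by the objective is shut out on age; the only discrepancy is possible extra infants.

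**When an eligible infant would cross the line.** 37+0 weeks is 37 × 7 = 259 days.

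- Born at 36+6: 36 × 7 + 6 = 258 days, and 259 − 258 = 1 day after birth.
- Born at 35+0: 35 × 7 = 245 days, and 259 − 245 = 14 days.
- Born at 26+0: 26 × 7 = 182 days, and 259 − 182 = 77 days.

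These figures show that the gap is logically possible, not that it is common. An infant must also still need non-invasive support on the day of study. The documents give no distribution of age at study or of duration of support, so the number affected cannot be derived.

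**Could it bias the comparison?** The session comprises 20 minutes of recording, two steps of 60 minutes and two 5-minute oscillometry measurements: 20 + 2 × 60 + 2 × 5 = 150 minutes at most. Age is effectively the same under both modes. The Randomization section has the envelope opened after enrolment, so age at entry cannot depend on the sequence allocated.

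**Does it touch the sample size?** The inputs in Statistical Analysis are means of 0.79 and 0.71, SDs of 0.14 and 0.13, a correlation of 0.5 and two-sided alpha of 0.05.

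- SD of the within-infant difference: √(0.14² + 0.13² − 2 × 0.5 × 0.14 × 0.13) = √0.0183 = 0.1353.
- Standardised effect: (0.79 − 0.71) / 0.1353 = 0.591. The plan states 0.59.
- Paired t-test, exact noncentral t, n = 25: power 0.81. The plan states "25 patients are needed for a two-tailed power > 0.80".

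The plan's figure reproduces, and no age limit enters it. This confirms only that the sample size does not depend on the point; it says nothing about which wording was meant.

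**The case for a change.** The strongest case for a change is that the primary objective states the trial's question and should name the infants actually studied. The text does not say that post-menstrual age means age at birth, and no other section closes the gap. Rewording the objective would cost almost nothing.

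Most of this stands as a description. The wording does differ, and a slip cannot be proved. A slip is nevertheless the likelier reading: the phrase follows the words for prematurity, uses the same 37-week threshold as the two sections that define the population, and sits in a document that its title page says was translated into English. The saturation bands do little to unsettle that reading. They use a different term, postconceptional age, and they govern infants already enrolled, not who may enter.

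The case does not show a benefit. Rewording the objective would alter no infant enrolled, no measurement and no analysis. Adding an age-at-study limit would alter enrolment, but at a recruitment cost that cannot be estimated, and nothing in the documents shows that the narrower population would answer the question better.

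Reporting age at study is useful to readers but needs no amendment. Gestational age at birth must be known to apply the inclusion criterion, and age at study must be known to choose the saturation band, so the information will be in hand for every infant.

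**Conclusion.** The inconsistency is real and minor, and the plan can stand. The inclusion criteria decide who enters, two sections and the enrolment statement agree with each other, and a single phrase in the objective departs from them. The effect on the within-infant comparison, the sample size and the power is nil. The effect on scope is unknown and may be zero.

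This rests on two assumptions: that enrolment follows the inclusion criteria, as Study Intervention says, and that the report describes its population by those criteria and gives age at study among the baseline characteristics, as analysts would ordinarily do. On that footing the phrase is a clerical looseness that readers can resolve for themselves.

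### No masking to ventilation mode, and no fixed breath or artefact rule, is described for the offline processing of the primary endpoint

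*Combined protocol and SAP*

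**What the plan says.** **Endpoint and source.** ENDPOINTS, PRIMARY names the endpoint as "Breath-by-breath variability of tidal breathing amplitude". Its signal comes from the cameras and skin markers: "Tidal breathing amplitude will be recorded continuously via two, high resolution, small cameras placed inside" the incubator. The same paragraph adds that flow, pressure, volume and electrical diaphragmatic activity are also recorded throughout.

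**Timing and method.** The timing and the choice of test are given as follows: "Data will be analysed *a posteriori* applying parametric or non-parametric statistical tools depending on the results of normal distribution test". The method for the longer-range structure of the signal is left partly open, since the plan says that "long term correlation properties will be studied by the DFA (Detrended Fluctuation Analysis) technique or similar".

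**Delimiting breaths.** Measured Variables and Data Analysis states: "The end-expiration will be identified by the two small, high resolution camera-based 3D sensors and the skin markers". It also states: "From the flow, pressure, volume and electrical diaphragmatic activity tracings, the breathing patterns will be measured". Short-term variability is to be summarised by a variation coefficient, which the plan labels SD.

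**Handling.** Under the caregiver-interventions endpoint, the plan counts comfort measures, interface adjustments and suctioning during each step.

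**Who knows what.** STUDY DESIGN calls the trial single-centre, randomised and cross-over, with no word on blinding. Under RANDOMIZATION, "Closed, opaque, sequentially numbered envelops will be then created by the collaborators" at the engineering department, and physicians open them after enrolment. The document nowhere mentions masking, coded files, an independent reader, or a rule for breath detection, artefact or segment choice.

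**The concern.** Opaque envelopes protect the allocation until enrolment. They do nothing for the assessment of outcome afterwards. Bedside staff must know the mode, because physicians open the sequence and the mode is set on the ventilator. Nothing in the plan keeps that knowledge from whoever later turns the recordings into a variability index.

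A variability index depends on which breaths and segments are kept, because a few large movements can dominate an SD. Handling can move both the infant and the markers, so some stretches of recording will probably raise the question of whether to keep them. If that is settled after the fact, without a written rule and with the mode known, even a slight difference in treatment between modes enters the primary contrast directly. Randomisation does not remove it, and a larger sample would not average it out.

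**Working it through.** **1. Reproduce the plan's own figure.** Inputs from STATISTICAL ANALYSIS: 0.79 ± 0.14 and 0.71 ± 0.13, correlation 0.5, two-tailed α = 0.05, power above 0.80, effect size 0.59, 25 patients.

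- SD of the paired difference = √(0.14² + 0.13² − 2 × 0.5 × 0.14 × 0.13) = √(0.0196 + 0.0169 − 0.0182) = √0.0183 = 0.1353.
- Effect size = (0.79 − 0.71) / 0.1353 = 0.08 / 0.1353 = 0.591, matching the stated 0.59.
- A two-sided paired t-test (noncentral t) first exceeds 80% power at n = 25, with power 0.81. The stated sample size reproduces.

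**2. Effect of a selection bias when the modes truly do not differ.** The bias sizes b are assumptions; the documents give none. Each b is an average shift, in one direction, of the per-infant difference between modes. Noncentrality = (b / 0.1353) × √25.

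| Assumed bias b | Share of planned 0.08 | b / 0.1353 | Noncentrality | Rejection rate at nominal 5% |
|---|---|---|---|---|
| 0.01 | 12.5% | 0.074 | 0.37 | 6.5% |
| 0.02 | 25% | 0.148 | 0.74 | 10.9% |
| 0.03 | 37.5% | 0.222 | 1.11 | 18.7% |

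**3. How little selection such a shift would need.** This is also hypothetical. Take the index to be a coefficient of variation of 0.75, the midpoint of 0.71 and 0.79 (the plan does not define the quoted index fully). Set mean amplitude to 1, so the mean square is 1 + 0.5625 = 1.5625. In one mode, keep a fraction p of movement-contaminated breaths at four times the mean amplitude; in the other, remove them.

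- p = 0.005: mean = 1.015; mean square = 0.995 × 1.5625 + 0.005 × 16 = 1.6347; SD = √(1.6347 − 1.0302) = 0.7775; coefficient = 0.766, a rise of 0.016.
- p = 0.01: mean = 1.03; mean square = 0.99 × 1.5625 + 0.01 × 16 = 1.7069; SD = √(1.7069 − 1.0609) = 0.8037; coefficient = 0.780, a rise of 0.030.

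Under these assumptions, treating one breath in 200 to one in 100 differently by mode gives a shift in the range of the table.

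**4. Can the processing be masked?** The amplitude signal and the end-expiratory points are both attributed to cameras and markers, which can in principle be processed without the ventilator display. Against that, ventilator signals appear in the primary-endpoint paragraph and are the stated source for breathing patterns, and they can reveal the mode. Masking is therefore practical for camera-based detection and artefact removal, and less so wherever the traces are viewed.

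**The case against.** The strongest reply is that the plan describes an instrument, not a reader: the sensors and markers identify end-expiration, and no manual selection is mentioned. If a fixed algorithm does all the work, masking adds little, and pre-specification would do most of the good even without it. This stands in part. The documents do not say how much is manual, so the risk cannot be asserted as fact. They do not specify an algorithm either, and thresholds and exclusions would still have to be set before the mode is linked. For that reason written rules belong in the fix alongside coding.

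Three further inferences are tempting and are not supported:

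- **That the analysts are unmasked.** The plan is silent. That bedside staff know the mode is a safe inference; that analysts know it is not stated.
- **That the engineering department holds the list and also processes the signals.** The plan attributes only the envelopes to that department. It names nobody as generating the list and nobody as processing the recordings.
- **That the primary endpoint comes from the cameras alone.** The ventilator signals listed beside it, and the use of tidal volume variation as the amplitude index in the sample-size paragraph, leave this open.

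The magnitude is also fairly challenged. The bias sizes have no source in the documents and must act in one direction on average across infants. The SD comes from a CPAP comparison of tidal volume with an assumed correlation, not from camera amplitude under these two modes. The smallest bias moves the error rate only from 5% to 6.5%, and the largest is over a third of the planned effect.

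**Conclusion.** The point holds as an omission: no masking is described for the offline processing of the primary endpoint, and no breath, artefact or segment rule limits the choices made there. The sample size is unaffected and reproduces at 25.

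The false-positive rates of about 6.5%, 11% and 19% illustrate scale under assumed biases of 0.01, 0.02 and 0.03, an SD of 0.135 and a paired t-test. A reader might take them as the trial's actual error rate, or as evidence that bias occurred; they are neither. The actual risk depends on how much of the processing is discretionary and who does it, which the plan does not say. Since the primary contrast is exposed and the safeguard is cheap, it is a worthwhile improvement.

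**What to change.** Add one paragraph to the analysis plan, to take effect before any recording is processed:

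1. Fix the rules for breath detection, artefact rejection and segment selection, including the treatment of handling periods.
2. Export the camera and marker signals for each one-hour step under a random code, without ventilator traces, mode or step order.
3. Run detection and exclusion on the coded files, and lock the per-step primary index before the key is linked.
4. State who holds the key and who processes the signals, and keep the sequence list from the latter.
5. State whether any part of the primary index needs the ventilator traces. If it does, that part cannot be fully masked and relies on the rules in item 1.

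Endpoints that need the traces, such as asynchrony, stay unmasked and should be reported as such.

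The cost is some file coding, separating camera from ventilator files, and key handling. Sample size, bedside procedures and infant care do not change. The mode may sometimes be guessed from the movement pattern, so the masking is partial and should be described that way.

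### An unspecified normality check chooses the primary test, while the sample size assumes the parametric test is always used; the named fallback, Friedman, has power of about 0.61 at 25 infants

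*Combined protocol and SAP*

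**What the plan says.** Under Endpoints, Primary, data are to be analysed after collection, "applying parametric or non-parametric statistical tools depending on the results of normal distribution test". The Measured Variables and Data Analysis part of the Statistical Analysis section gives the two branches: "ANOVA or Friedman test for repeated measurements as appropriate according to data distribution will be used to verify differences". Neither place names the normality test, its significance level or the quantity it is applied to (values in each mode, all values together, or within-infant differences). No other primary analysis is given.

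The sample size paragraph in Statistical Analysis says "25 patients are needed for a two-tailed power > 0.80" at a 5% significance level, "hypothesizing a normal distribution and an effect dimension of 0.59". The effect comes from two published conditions (0.79 ± 0.14 and 0.71 ± 0.13), "considering a correlation among groups = 0.5". It makes no allowance for a switch to Friedman.

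**The concern.** In a two-mode cross-over with one value per mode, the comparison rests on each infant's NAVA minus PC difference. Only those differences need to be near normal for the paired test. The enrolled population covers any gestation below 37 weeks, so the values within a mode could be skewed because infants differ from one another, while the differences are well behaved. A check on raw values could then discard a valid test in favour of a weaker one.

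Two things are at stake. The stated power belongs to a test that the plan does not commit to. And the choice of test for the only primary comparison is made once the data are in, by a rule too loosely defined for anyone to reproduce.

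**Working it through.** **Inputs from the sample size paragraph:** means 0.79 and 0.71, SDs 0.14 and 0.13, correlation 0.5, two-sided α = 0.05, n = 25.

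**1. Reproduce the plan's figure.**
- SD of differences = √(0.14² + 0.13² − 2 × 0.5 × 0.14 × 0.13) = √0.0183 = 0.1353.
- Paired effect = 0.08 / 0.1353 = 0.591, which matches the stated 0.59.
- Paired t power (noncentral t) is 0.790 to 0.792 at n = 24 and 0.808 to 0.810 at n = 25. So 25 is the smallest n above 0.80, with about one point to spare.
- With two modes and one value each, repeated-measures ANOVA gives the same result as the paired t test (F = t²).

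**2. Power of the named fallback.** With two conditions and one value per condition, Friedman uses only the sign of each difference.
- Probability that a difference favours the better mode = Φ(0.59) = 0.72.
- Rejection needs at least 18 of 25 differences in one direction (actual α = 0.043).
- Power = P(Binomial(25, 0.72) ≥ 18) = 0.61. About 40 infants would be needed for 0.80.

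**3. Power of the two-stage rule on normal data.** This was simulated from the planning values (60,000 trials, Monte Carlo standard error about 0.0016). Shapiro-Wilk at 5% is an assumption, because the plan names no test. The fixed paired t gave 0.809 in the same runs.

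| Variable checked | Sent to fallback | Power, Friedman fallback | Power, Wilcoxon fallback |
|---|---|---|---|
| Each mode | 10% | 0.790 | 0.807 |
| Pooled values | 5% | 0.798 | 0.808 |
| Differences | 5% | 0.802 | 0.809 |

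A rough check of the first row: 0.90 × 0.81 + 0.10 × 0.61 = 0.79. With no true difference, the rule's rejection rate with the Friedman fallback was 0.049 to 0.052.

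**4. Skewed infants, normal differences (assumed; the documents give no shape).** Each infant has a gamma component shared by both modes, with variance 0.5 × 0.14 × 0.13 = 0.0091. Independent normal parts have variances 0.14² − 0.0091 = 0.0105 and 0.13² − 0.0091 = 0.0078. The differences are then exactly normal with variance 0.0105 + 0.0078 = 0.0183, as planned. With gamma shapes 4, 2, 1 and 0.5 and each mode checked (20,000 trials each):
- 18% to 41% of trials go to Friedman;
- power of the rule is 0.772, 0.762, 0.749 and 0.721, against 0.807, 0.807, 0.809 and 0.805 for the fixed paired t.

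A separate simulation at shapes 4, 1 and 0.5 gave 0.777, 0.747 and 0.734 when each mode was checked, 0.782, 0.750 and 0.736 when pooled values were checked, and about 0.80 throughout when differences were checked.

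**The case against.** The strongest reply is that the plan is silent on what is checked, and silence is not a wrong rule. That stands. A reader might infer that raw values will be tested, but the documents neither name nor exclude the within-infant difference, and if differences are checked the loss is under one point.

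A reader might also conclude that power above 0.80 is not delivered even on normal data. The documents do not support this as a flat statement. It holds only if raw values are checked and Friedman is the fallback, and then by at most one point below 0.80, which is small beside the uncertainty in a correlation of 0.5 and SDs taken from a different comparison. At n = 26 every version of the rule exceeds 0.80.

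Running both tests in every simulated trial gives different verdicts in 23% to 24% of trials, which invites the reading that the choice matters that often. It does not. On normal data with each mode checked, only 10% of trials reach Friedman, and the rule's verdict differs from the fixed paired t in about 2%.

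The larger losses in step 4 rest on skew that no document reports. More extreme skew than that should not be built in without a source: the planning values imply a total coefficient of variation of about 0.14 / 0.79 = 18%.

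Finally, Study Duration/Time Points lists several assessments within each hour. If these entered the Friedman test as separate measurements, it would no longer be the sign test, and 0.61 and the figures built on it would not apply. The documents do not settle this. It limits the numbers and is a further reason to state the primary comparison exactly.

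**Conclusion.** The point holds as an efficiency and pre-specification issue. The primary test is left to an undefined check on the data, and the sample size does not cover the fallback the plan names.

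- **If Friedman is used:** power about 0.61 at n = 25, given one value per mode per infant.
- **Whole rule, normal data:** about 0.79 to 0.80, against 0.81 for a fixed paired test (Shapiro-Wilk at 5% assumed).
- **Whole rule, raw values checked, skewed infants with normal differences:** about 0.72 to 0.78, a loss of roughly 3 to 8 points. This scenario is assumed.
- **Type I error:** near 0.05, so there is no case for inflated false positives.

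The sample size calculation itself is correct for a paired test that is always run. The change is worth making because it costs almost nothing and makes the stated power apply to the test performed.

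**What to change.** Remove the normality pre-test for the primary endpoint and state something like: *The primary analysis compares NAVA-NIV with PC-NIV using one within-infant difference per infant, by a two-sided paired t test at 5% (equivalently, the mode term of the repeated-measures ANOVA), whatever the distribution within each mode. A Wilcoxon signed-rank or sign-flip permutation test on the same differences is a sensitivity analysis.* Friedman should not be used for this comparison. The text should also say how the recordings in each hour are reduced to one value per mode.

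If a distribution check is kept, name the test and its level, apply it to the within-infant differences, and make signed-rank the fallback; power on normal data is then 0.809.

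The cost is a few sentences, with no new data and no change in sample size. The downside is that with heavily skewed differences a rank test could be somewhat more powerful; the sensitivity analysis would show this.
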